5.1.5 Physical Examination Findings

Physical Examination in this study is performed at Visit 1.

Collected Variables:

- General appearance of the system (categories: skin, eyes, ears-nose-throat, breast, head&neck, lungs, heart, abdomen, extremities, limphonodes, musculoskeletal, peripheral vascular, genitourinary, other) [CRF – Visit 1]
- normal/abnormal/not assessed statement [CRF – Visit 1]
- abnormalities (text) [CRF – Visit 1]

Derived Variables: Not applicable

Imputations for missing values: Not applicable

Analysis Sets to be used for:	Tables	Safety set
	Listings	Safety set
	Figures	Not applicable

Physical Examination Findings will be summarized as follows:

	Form	Form No.	1M-DMST-011-01-A1
	Statistical Analysis Plan	Page	Page 18 of 69
		Effective Date	07/05/2018

Table 9. Physical Examination Findings by Body System (Safety set) Number and percent of subjects with abnormal findings for each body system of physical examination will be tabulated at visit 1 by treatment group.

In addition, physical examination data will be presented as follows:

Listing 10. Physical Examination Physical examination findings will be presented by subject.

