3.2 Flow Chart

	V1 Screening & treatment start					V2	V3	V4	V5 (EOS)	
	Day -7					Day 0	Day 7	Day 14	Day 28	
	moment 0	h 1	h 2	h 4	h 8	h 12				
ICF	x									
Incusion/Exclusion criteria check	x									
Vital signs	x	x	x	x	x	x	x	x	x	x
Physical examination	x						x	x	x	x
Medical history	x									
Concomitant medication	x						x	x	x	x
Blood sampling	x	x	x	x	x	x	x	x	x	x
CoQ10 intake	x						AB	AB	AB	AB
Pharmacokinetics		x	x	x	x	x	x	x	x	x
Adverse events		x	x	x	x	x	x	x	x	x

	Study Title	Bioavailability Study of COQUN ORAL FORMULATION (CoQ10) administered in Healthy Adults (CoQ10-01)		
	Study ID	VF-BAQ10/2018	Sponsor:	VISUFARMA SpA
	Date	March 03, 2018	Vers.	Final

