7.2 VARIABLES

Primary Variable

Pharmacokinetic properties:

- Area under the curve (microg/ml x h): ≥ 5
- Cmax: $\geq 0,8$
- Tmax: ≥ 3
- elimination half-life (t 1/2)

Secondary Variable(s)

The secondary variables are the ones regarding safety which will be monitored through vital signs, physical exams, ECGs, clinical laboratory tests and adverse events, as follows:

- following a single oral dose of 100mg COQUN ORAL FORMULATION
- in 1 month period of daily oral intake of 100mg OD or BID COQUN ORAL FORMULATION

Symptoms and signs like mild insomnia, elevated levels of liver enzymes, rash, nausea, upper abdominal pain, dizziness, sensitivity to light, irritability, headache, heartburn, and fatigue will be closely monitored.

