10.6.6 Body measurements

Subject's body height and weight will be measured at screening visit. During the ambulatory visits only the body weight will be measured.

10.6.7 12 lead ECG

A standard 12-lead ECG will be performed after the subject has rested for at least 5 minutes in the supine position at screening and at end of study.

The time of ECG and the overall interpretation (normal, clinically insignificant abnormality, clinically significant abnormalities) will be recorded. Copies of the tracings must company the corresponding CRF.

	Study Title	Bioavailability Study of COQUN ORAL FORMULATION (CoQ10) administered in Healthy Adults (CoQ10-01)		
	Study ID	VF-BAQ10/2018	Sponsor:	VISUFARMA SpA
	Date	March 03, 2018	Vers.	Final

The subject number, the actual date and time of the tracing and the study code must appear on each page of the tracing. The tracings must be signed by the study investigator performing the interpretation.

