12.8 Analysis of Secondary Variables

The secondary variables are the ones regarding safety which will be monitored through vital signs, physical exams, ECGs, clinical laboratory tests and adverse events, as follows:

- Following a single oral dose of 100mg COQUN ORAL FORMULATION
- in 1 month period of daily oral intake of 100mg OD or BID COQUN ORAL FORMULATION

Symptoms and signs like mild insomnia, elevated levels of liver enzymes, rash, nausea, upper abdominal pain, dizziness, sensitivity to light, irritability, headache, heartburn, and fatigue will be closely monitored.

At each time point and for each group, descriptive statistics will be provided. See section **12.9** for details.

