6. CHANGES TO THE ANALYSIS AS LAID DOWN IN THE PROTOCOL AND AMENDMENTS

No changes to the analysis as laid down in the protocol were made.

1MED Regulatory & Clinical Development	Form	Form No.	1M-DMST-011-01-A1
	Statistical Analysis Plan	Page	Page 31 of 69
		Effective Date	07/05/2018

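### The SAP tabulates physical examination only at the pre-dose Visit 1 and has no ECG output, although the protocol makes both secondary safety variables, and SAP section 6 declares no change

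*SAP*

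**What the plan says.** **Protocol.** Section 12.8 says: "The secondary variables are the ones regarding safety which will be monitored through vital signs, physical exams, ECGs, clinical laboratory tests and adverse events". Section 7.2 gives the same list and ties it to two periods: "following a single oral dose of 100mg COQUN ORAL FORMULATION", and the month of daily OD or BID intake. Section 12.8 then plans descriptive statistics for each group at each time point. In the flow chart (3.2), the "Physical examination" row is marked at V1 moment 0 and at V2, V3, V4 and V5. Section 10.6.7 calls for a 12-lead ECG "in the supine position at screening and at end of study", with the overall reading graded as normal, clinically insignificant abnormality or clinically significant abnormality.

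**SAP.** Section 5.1.5, under Baseline Characteristics, states: "Physical Examination in this study is performed at Visit 1". Every field is sourced from the Visit 1 CRF, and the Table 9 findings "will be tabulated at visit 1 by treatment group". Section 5.2.2 repeats the protocol's sentence on secondary variables but lists only vital signs and adverse events. The indexes of tables, listings and figures (8.1) contain no ECG item. Section 6 states: "No changes to the analysis as laid down in the protocol were made".

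**The concern.** Safety and tolerability after the single dose and over the month of intake are the two secondary objectives (Protocol 7.1, SAP 2.1). The examination that the SAP tabulates is one of the screening procedures in Protocol 10.5.1. It comes before the first capsule and before randomisation, so a table of it by arm describes baseline balance and says nothing about tolerability.

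For these two variables, an analyst who follows the SAP produces no post-dose summary by arm. The study is unblinded (SAP 2.6) and adverse event reporting involves judgement, so a scheduled summary by arm would be a useful check on what was reported. Because section 6 declares no change, a reader of the study report would not learn that two protocol-named safety variables had been dropped.

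**Working it through.** The plan gives no figure to reproduce. The check compares the documents and counts scheduled assessments.

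**Side by side**

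| Item | Protocol | SAP |
|---|---|---|
| Physical examination as secondary variable | Yes (7.2, 12.8) | Not in 5.2.2 |
| Examination time points | V1 to V5 (flow chart) | V1 only (5.1.5, Table 9) |
| ECG as secondary variable | Yes (7.2, 12.8) | Not in 5.2.2 |
| ECG time points | Screening and end of study (10.6.7) | No section, table, listing or figure |
| Vital signs | V1 to V5 | By visit, with change from baseline (Table 24) |
| Declared change | – | None (section 6) |

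Table 24 shows that the SAP has no general policy against by-visit safety tables.

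**Inputs for the count**
- Subjects: 24, or 12 per arm (Protocol 12.3), assumed all to complete.
- Examinations per subject: 5 (flow chart). One is before any dose (V1), one follows the single dose and precedes multidose intake (V2, Day 0), and three fall during multidose intake (V3 to V5).
- ECGs per subject: 2 (10.6.7), of which one is post-treatment.

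**Examinations**
- Scheduled: 24 × 5 = 120.
- Tabulated by the SAP: 24 × 1 = 24, or 24/120 = 20%.
- Untabulated: 120 − 24 = 96, all after the first dose.
- Of these, V2 contributes 24 × 1 = 24 and V3 to V5 contribute 24 × 3 = 72 (12 × 3 = 36 per arm).

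**ECGs**
- Scheduled: 24 × 2 = 48. Analysed: 0.
- Post-treatment: 24 × 1 = 24 (12 per arm). The other 24 are screening tracings.

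**What still reaches the output.** Protocol 11.1.1 counts clinically significant changes from baseline in the examination or ECG as adverse events. Protocol 10.6.4 sends significant later examination findings that meet the adverse event definition to the CRF. SAP Tables 18 to 23 and Listing 18 then cover them.

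**What does not.** Three things have no output: the by-visit examination and ECG summaries by arm, ECGs in the clinically insignificant category that 10.6.7 collects by design, and examination findings not written up as adverse events.

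**The case against.** The strongest reply is that the adverse event route already captures what matters. A reader of the SAP might infer that post-treatment examination and ECG findings go wholly unanalysed. The documents do not support that, because clinically significant changes are adverse events by definition and are summarised by arm. This part of the reply stands and limits the consequence. It does not close the gap. The adverse event tables have no place for an insignificant ECG abnormality, and 10.6.4 asks subjects to enter later findings in their diary before the investigator reports them, which is a weak route for signs that a clinician detects.

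The protocol's schedule is also less settled than its flow chart suggests. The V2 and V3–V5 procedure lists (10.5.2, 10.5.3) omit both assessments, the flow chart has no ECG row, and the safety lists in the synopsis and 12.9.1 omit ECG. Section 12.8 refers to 12.9 for details, and 12.9 has subsections only for adverse events and laboratory data. This stands too. The protocol needs reconciling, but its inconsistency does not make section 6 of the SAP correct: 7.2, 12.8 and 10.6.7 are explicit, and 12.9.1 keeps physical examination.

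Three narrower points also stand. Only V3 to V5 bear on the multidose month, so 96 examinations and 48 ECGs should not be read as multidose counts. The Listing 10 shell already has a Visit column, so its limit lies in the Visit 1 source tags of 5.1.5. Finally, the study is exploratory, with 12 per arm and no prespecified hypotheses, so nothing here touches the pharmacokinetic conclusion.

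**Conclusion.** The point holds as an undeclared mismatch between protocol and SAP on two named secondary safety variables. As written, the SAP gives no post-dose summary of physical examination and no ECG output at all, and its statement that nothing changed is wrong.

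Assuming 24 completers and the flow chart's schedule, 96 of 120 examinations have no table: 24 at V2 after the single dose and 72 during multidose intake. None of the 48 ECGs is analysed, 24 of them post-treatment. Dropouts would lower these counts, although Protocol 10.7 asks for both assessments at premature termination.

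The loss is confined to by-visit summaries by arm, insignificant ECG abnormalities and findings not reported as adverse events. A reader might also infer from SAP 5.1.5 that no later examinations were done or recorded. The documents do not settle this, because the CRF is not among them. The SAP's own flow chart could not be read in the available text and is not relied on. The primary analysis is unaffected; this should be corrected before database lock.

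**What to change.** 1. Extend SAP 5.1.5, Table 9 and the source tags of Listing 10 to V1 to V5 by treatment group. Use the baselines in SAP 4.4: V1 for the single-dose phase and V2 for the multidose phase. A shift from V1 alone would conflict with the V2 baseline already used for vital signs in Table 24.
2. Add an ECG table and listing using the three categories of Protocol 10.6.7, screening against end of study, by group. ECG has no V2 time point, so screening is the only available baseline.
3. Add both variables to SAP 5.2.2.
4. Reconcile Protocol 10.5.2, 10.5.3, the flow chart and 12.9.1 with 10.6.7 and 12.8, so that one schedule governs.
5. Check the CRF. If it does not hold V2–V5 examinations or ECGs, table shells cannot repair the gap, and SAP section 6 must be corrected to declare the omission with a reason.

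If the data are collected, the cost is an extended Table 9, one ECG table, one ECG listing and short text edits. If they are not, CRF pages would also be needed, or the declaration in step 5. The SAP introduction requires sign-off before hard lock, so this should be settled by then.

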5.1.6 Pregnancy

Pregnancy data in this study is recorded at Visit 1.

Collected Variables:

- Pregnancy test performed (categories: Done, Not Done, Not Applicable) [CRF – Visit 1]
- Pregnancy test result (categories: Positive, Negative) [CRF – Visit 1]

Derived Variables: Not applicable

Imputations for missing values: Not applicable

Analysis Sets to be used for:	Tables	Safety set
	Listings	Safety set
	Figures	Not applicable

Pregnancy data will be summarized as follows:

Table 10. Pregnancy test (Safety set) Number and percent of subjects with a positive result in the pregnancy test will be tabulated at visit 1 by treatment group.

In addition, physical examination data will be presented as follows:

Listing 11. Pregnancy Pregnancy data will be presented by subject.

5.1.7 Medical History and Trial Specific Diseases

5.1.7.1 Medical History

Medical history is defined as any condition, except for the study indication, that the subject may have had prior to enrollment in the study, including any chronic conditions diagnosed prior to entry in the study, for example, diabetes. Medical history will be reported on a by-subject basis. Medical history findings will be presented in disorder categories as reported in the CRF.

Collected Variables:

- Disorder (categories: infections and infestations, neoplasms, blood and lymphatic system, immune system disease, endocrine disorders, metabolism and nutrition disorders, nervous system disorders, ear and labyrinth disorders, cardiac disorders, vascular disorders, respiratory, thoracic and mediastinal disorders, gastrointestinal

	Form	Form No.	1M-DMST-011-01-A1
	Statistical Analysis Plan	Page	Page 19 of 69
		Effective Date	07/05/2018

disorders, hepatobiliary disorders, skin and cutaneous tissue disorders, musculoskeletal and connective tissue disorders, renal and urinary disorders, reproductive system disorders, injury, poisoning and procedural complications, surgical procedures, other)

- Has the patient experienced the disorder (yes, no) [CRF – Visit 1]
- Details (free text) [CRF – Visit 1]
- Start date of event [CRF – Visit 1]
- Stop date of event [CRF – Visit 1]
- Event ongoing (yes, no) [CRF – Visit 1]

Derived Variables: Not applicable

Imputations for missing values:

Missing or partial dates for medical history will not be completed, for example, if only a month and year are available as --FEB2005, the day will not be imputed in order to complete the date. If “End Date” information is not available, it will be assumed that the finding is “Ongoing” at the time of enrollment in the study.

Analysis Sets to be used for:	Tables	Safety analysis set
	Listings	Safety analysis set
	Figures	Not applicable

Medical history findings will be summarized by treatment group as follows:

Table 11. Medical History (safety set)	The number of subjects with at least one medical history finding will be presented by default summary statistics, where the percentage of subjects is calculated relative to the total number of subjects in the safety analysis set.
---	---

All medical history will be presented in subjects data listings as follows:

Listing 13. Medical History	Medical history findings will be presented by-subject and within subjects by disease category of each medical history finding as a subject data listing.
------------------------------------	--

5.1.7.2 Trial Specific Diseases

Not applicable

5.1.8 Prior and Concomitant Medication

Medications will be reported as recorded in CRF.

Collected Variables:

- Medication generic name (text) [CRF – Cumulative Concomitant Medication Form]
- Dose administered [CRF – Cumulative Concomitant Medication Form]
- Unit (standard dosage units, e.g., mg, mcg, cc, mL, IU, etc.) [CRF – Cumulative Concomitant Medication Form]
- Frequency (categories: od=once daily / bid=twice daily / tid=3 times daily /qid=4 times daily / 5/day=5 times daily /prn= as required; etc) [CRF – Cumulative Concomitant Medication Form]
- Dosage form (categories: tab= tablet; cap = capsule, oint = ointment, supp = suppository, aer = aerosol, susp = suspension, spray, patch, syrups, drops, vials, gel, cream, etc.) [CRF – Cumulative Concomitant Medication Form]

	Form	Form No.	1M-DMST-011-01-A1
	Statistical Analysis Plan	Page	Page 20 of 69
		Effective Date	07/05/2018

- Route of administration (categories: os= oral / iv= intravenous / sc= subcutaneous / im= intramuscular / inh= inhalation / top= topical/ sl= sublingual/ oth= other) [CRF – Cumulative Concomitant Medication Form]
- Indication [CRF – Cumulative Concomitant Medication Form]
- Start date of medication [CRF – Cumulative Concomitant Medication Form]
- Stop date of medication [CRF – Cumulative Concomitant Medication Form]
- Medication ongoing (yes, no) [CRF – Cumulative Concomitant Medication Form]

Derived Variables:

- **Prior medications** are defined as those starting and ending prior to the first administration of investigational study medication.
- **Concomitant medications** are defined as medications started at or after first administration of investigational study medication and include medications started prior to the first administration of investigational study medication but continued during the study.

Imputations for missing values: Not applicable

Analysis Sets to be used for:	Tables	Safety analysis set
	Listings	Safety analysis set
	Figures	Not applicable

Concomitant and prior medication will be summarized by treatment group as follows:

Table 12. Concomitant and Prior Medication (Safety set)	The number of subjects with at least one concomitant/prior medication will be presented by default summary statistics, where the percentage of subjects is calculated relative to the total number of subjects considered valid for the safety analysis set.
--	--

All medications entered on the “Cumulative Concomitant Medication” CRF form will be presented in subject data listings as follows:

Listing 12. Prior and Concomitant Medications	By-subject and within-subject by ascending start date of medication use will be presented for those subjects who were allocated to treatment and received at least one dose of investigational study medication.
--	--

5.2 Efficacy Analysis

5.2.1 Primary Efficacy Analysis

The primary objective of this study is to evaluate the best dosage between 100mg once daily or 100mg twice daily for COQUN ORAL FORMULATION in order to reach a level of plasma concentration which might assure its antioxidant effect if taken on a regular basis.

The following pharmacokinetic properties will be evaluated:

- Area under the curve (microg/ml x h)
- C_{max}
- T_{max}
- Elimination half-life (t_{1/2})

Collected Variables

- Plasma concentration of coenzyme Q10 [CRF – Visit 2, 3, 4, 5]

	Form	Form No.	1M-DMST-011-01-A1
	Statistical Analysis Plan	Page	Page 21 of 69
		Effective Date	07/05/2018

Derived Variables

Derived variables are shown in Image 1 and are the following^[2,3]:

- AUC_t
The area under the plasma concentration curve to the last quantifiable concentration (C_t) at time t (AUC_t) will be determined by linear trapezoidal rule. The trapezoidal rule is a method used to numerically approximate the area under the concentration by time curve obtained by summing the area of all trapezoids constructed under the curve. Each trapezoid's area is obtained as:

$$\frac{(C_i + C_{i+1}) * (T_{i+1} - T_i)}{2}$$

where C_i is the concentration at time i (where i is any timepoint before the last observed timepoint T_t), C_{i+1} is the concentration at the following timepoint, T_i is the timepoint i and T_{i+1} is the following timepoint.

- C_{max}
Maximum concentration in the plasma (C_{max}) is obtained directly from the data being the highest plasma concentration value.
- T_{max}
 T_{max} is the collection time in which the maximum concentration is observed and is related to the drug absorption speed.
- $t_{\frac{1}{2}}$
The terminal half-life is defined as the time required for the plasma concentration of a drug to decrease 50% in the final stage of its elimination; this parameter is computed with the formula^[2]:

$$t_{\frac{1}{2}} = \frac{\ln 2}{\lambda_z}$$

where λ_z is the smallest elimination rate constant observed which is obtained as the ratio of clearance and volume of distribution. Clearance is calculated as the ratio of dose and AUC while volume of distribution is obtained as dose divided by concentration at time 0 that is the concentration registered after the first intake of coenzyme (in the single dose time 0 is hour 1, in the multidose phase time 0 is visit 2).

[figure not shown]

Image 1. Pharmacokinetic parameters

	Form	Form No.	1M-DMST-011-01-A1
	Statistical Analysis Plan	Page	Page 22 of 69
		Effective Date	07/05/2018

Analysis of Primary Efficacy variable:

Descriptive statistics such as mean \pm standard deviation, median with interquartile range, minimum, maximum and coefficient of variation will be presented for the plasma concentration of coenzyme Q10 at each time point in the entire sample of subjects. 95% confidence interval will be provided as well.

An explorative analysis on gender will be performed showing descriptive statistics for plasma concentration of coenzyme Q10 by gender. The effect of gender will be explored by means of a mixed model for repeated measures with covariates *gender*, time and the interaction term *gender*time*.

Descriptive statistics will be also provided for the plasma concentration of coenzyme Q10 at each time point by treatment group.

Change of plasma concentration versus baseline (i.e. change versus visit 2 values) will be computed for each study visit both for the whole sample and by treatment group.

Change will be computed in the following way:

$$\text{Change (\%)} = \frac{\text{Value at Visit X} - \text{Baseline Value}}{\text{Baseline Value}} \times 100$$

Area under the curve, maximum concentration in the plasma, time of maximum concentration and terminal half-life will be presented descriptively on the original scale.

95% confidence interval will be provided for the means of 100mg OD and 100mg BID for COQUN ORAL FORMULATION for the parameters AUC_t , C_{max} , T_{max} and terminal half-life. A Student t-test for unpaired data will be performed in order to detect differences between the two groups in the pharmacokinetics parameters.

A concentration by time graph will be presented for the multidose phase by treatment group in order to have a graphical visualization of the pharmacokinetics properties over time.

Line graphs will be provided for the concentration of coenzyme Q10 in the whole sample and by gender.

In performing statistical analysis, it is important to assess the statistical outliers. In fact, inclusion or exclusion of outlying subjects may lead to a different conclusion in assessment of differences in bioavailability between two formulations. It is therefore important to identify these outliers and study their effects.

Primary endpoint will be evaluated on the ITT population and analysis will be replied on the PP population. Results obtained on the PP population will be considered as supportive of those obtained on the ITT set.

Imputations for missing values: No imputation of missing data will be performed

Analysis Sets to be used for:	Tables	ITT and PP analysis set
	Listings	ITT analysis set
	Figures	ITT and PP analysis set

	Form	Form No.	1M-DMST-011-01-A1
	Statistical Analysis Plan	Page	Page 23 of 69
		Effective Date	07/05/2018

Primary efficacy variable will be summarized by treatment group as follows:

Table 13. Primary Efficacy Variable at Each Study Visit (ITT Analysis Set)

Default summary statistics per treatment group for the primary efficacy variable (Plasma concentration of Coenzyme Q10) at each study visit will be presented for the ITT analysis set.

This table will be replied on the PP analysis set.

Table 14. Plasma concentration of coenzyme Q10 by gender (ITT Analysis Set)

Default summary statistics per gender for the primary efficacy variable (Plasma concentration of Coenzyme Q10) at each study visit will be presented for the ITT analysis set.

This table will be replied on the PP analysis set.

Table 15. Change versus baseline by Treatment (ITT Analysis Set)

Default summary statistics per treatment group for the change versus baseline at each study visit will be presented for the ITT analysis set.

This table will be replied on the PP analysis set.

Table 16. Pharmacokinetic Parameters by Treatment (ITT Analysis Set)

Default summary statistics per treatment group for each pharmacokinetic parameter will be presented for the ITT analysis set.

This table will be replied on the PP analysis set.

Table 17. Confidence Interval and Results of T-test for Primary Efficacy Variable (ITT Analysis Set)

Confidence interval at 95% will be presented for the means of the pharmacokinetics parameters in the two groups in the ITT analysis set. The table also contains the result of the Student t-test detecting the differences between the two groups.

This table will be replied on the PP analysis set.

A Primary efficacy variable will be presented in subject data listings as follows:

Listing 16. Listing of Primary Efficacy Variable

A listing of the values for the primary efficacy variable (Plasma concentration of Coenzyme Q10) as used in the primary analysis, sorted by screening number and within subjects by time point will be presented.

Listing 17. Listing of Pharmacokinetic parameters

A listing of the values for the pharmacokinetic parameters as used in the primary analysis, sorted by screening number will be presented.

The primary endpoint will be presented in a graph as follows:

Figure 3. Concentration by time plot (ITT Analysis Set)

A concentration by time graph will be presented for the multidose phase in the ITT analysis set. This plot will be replied in the PP analysis set.

Figure 4. Concentration by time plot by treatment group (ITT Analysis Set)

A concentration by time graph by treatment group will be presented for the multidose phase in the ITT analysis set. This plot will be replied in the PP analysis set.

Figure 5. Concentration by time plot by gender (ITT Analysis Set)

A concentration by time graph by gender will be presented for the multidose phase in the ITT analysis set. This plot will be replied in the PP analysis set.

